# **10.6** Appendix 6: Prohibited concomitant medications

Table 10-4: Prohibited concomitant medication potentially confounding efficacy

Prohibited from the time shown until 1 week after the last dose of study drug		
	Hormonal therapies	
From 1 week prior to Baseline Visit	Vaginal hormonal products (rings, creams, gels)	
From 4 weeks prior to Baseline Visit	Transdermal estrogen alone or estrogen/progestin products	
From 8 weeks prior to Baseline Visit	
 
Oral estrogen and/or progestin therapy
 
Intrauterine progestin therapy
 
	
From 12 weeks prior to Baseline Visit	Progestin implants and estrogen alone injectable drug therapy	
From 24 weeks prior to Baseline Visit	Estrogen pellet therapy or progestin injectable drug therapy	
	Non-hormonal therapies	
From 12 weeks prior to Baseline Visit	adjuvant endocrine therapy other than tamoxifen, aromatase inhibitors or GnRH analogues (e.g., CDK 4/6 inhibitor, toremifene, fulvestrant). The participant is allowed to switch to CDK 4/6 inhibitors after 12 weeks of treatment with the study intervention (i.e., after the placebo-controlled period ends).	
From 4 weeks prior to Baseline Visit	Antidepressant drugs:  Participants are permitted to continue to use antidepressant drugs and over the counter/herbal treatments (see details below) when the dose has been stable for at least 4 weeks and when it is anticipated to be stable for the duration of the study. In addition, the drug has been prescribed solely for the management of another disorder (e.g., neuropathic pain, depression).  Participants are not allowed to start with these drugs during the study:  • Anti-depressant drugs with effect on vasomotor symptoms (e.g., paroxetine, other including selective serotonin reuptake inhibitors, serotonin norepinephrine reuptake inhibitors and tri-cyclic antidepressants, alpha agonists [clonidine], methyldopa, gabapentin, pregabalin, medicinal cannabis or derivatives)  • Over the counter/herbal treatments including traditional Chinese medicine for treatment of vasomotor symptoms.  Others:  • Oxybutynin/ Oxybutynin hydrochloride	

CDK = Cyclin-dependent kinases, CYP2D6 = Cytochrome P450 2D6, GnRH = Gonadotropin-releasing hormone

10 MAY 2023 Page: 86 of 97

[figure not shown]
[figure not shown]

Table 10-6 and Table 10-7 list examples of the most common medication regarded as

10 MAY 2023 Page: 87 of 97

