6.4.3. Intake of prohibited concomitant medication having impact on efficacy

Drug groupings, individual drugs and manual review will be used to identify whether any prohibited concomitant medication as defined in the protocol were used that influence efficacy. All here listed drug groupings/ drug names were reported in OASIS 1-4 studies as of finalization of this statistical analysis plan, although other medications may also be prohibited per the protocol.

- 1. For the change from baseline at Week 1 any intake of prohibited medication during Week 1 that has an effect on HF will be considered an intercurrent event.
- 2. For weeks 4, 8, and 12, not only intake in the respective week but also, intake that occurred prior to week 4, 8, and 12 should be considered as an intercurrent event if within the washout period of the prohibited drug.

A similar approach will be used for the endpoints related to sleep quality (mean change in PROMIS SD SF 8b total score from baseline) and to the menopause related quality of life (mean change in MENQOL total score from baseline) with respect to any prohibited medication that has an effect on sleep quality and menopause related quality of life, respectively.

The list of prohibited concomitant medication together with the assumed relevant time period for their effect will be reviewed during blind review of the data and finalized prior to unblinding.

^b No further differentiation if duration of impact is longer than 12 weeks since ICEs are considered in the analysis only for the first 12 weeks of the study.

version 3.0 Page: 73 of 87

Table 6–5: Preliminary list of prohibited concomitant medication by drug grouping (can be updated during the blind review meeting)

Any additional condition, so that considere d as prohibite d and considere d as intercurre nt event	DGCODEL0	DGNA ME0	DGCODE L1	DGNAME1	DGCODEL2	DGNAME2	Duration of impact with respect to efficacy ^a (considered up to 12 weeks ^b)
If newly started or dose modified or stopped during the first 12 weeks of study period			5	Hormone replacement therapy	2	Oestrogens	1, From 1st dose to 4 weeks after the last dose if the route is vaginal, intravaginal, cutaneous, nasal or transdermal. 2, From 1st dose to 8 weeks after the last dose if the route is oral, sublingual or intrauterine, 3, From 1st dose to 12 weeks or longer if the route is subcutaneous or intradermal.

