If newly started or dose modified or stopped during the first 12 weeks of study period			5	Hormone replacement therapy	3	Progestogens	1, From 1st dose to 4 weeks after the last dose if the route is vaginal, intravaginal, cutaneous, nasal or transdermal. 2, From 1st dose to 8 weeks after the last dose if the route is oral, sublingual or intrauterine, 3, From 1st dose to 12 weeks or longer if the route is subcutaneous,

Statistical Analysis Plan BAY 3427080 / 21656 version 3.0

version 3.0 Page: 74 of 87

							intradermal or intramuscular.
Any other than tamoxifen or aromatase inhibitor or GnRH agonists and GnRH antagonist; if newly started or dose modified or stopped during the first 12 weeks of study period			772	Cancer therapies	738	Endocrine antineoplastic therapy	From 1st dose to 12 weeks after the last dose (All other cancer therapies are excluded, only tamoxifen, aromatase inhibitors, GnRH agonists and GnRH antagonist are allowed.°)
If newly started or dose modified or stopped during the first 12 weeks of study period	1633	Drugs for psychi atric disord ers	111	Antidepressants	114	Monoamine oxidase (MAO) inhibitors, non- selective	From 1st dose to 4 weeks after the last dose
If newly started or dose modified or stopped during the first 12 weeks of study period	1633	Drugs for psychi atric disord ers	111	Antidepressants	115	Monoamine oxidase A (MAO-A) inhibitors	From 1st dose to 4 weeks after the last dose

Statistical Analysis Plan BAY 3427080 / 21656 version 3.0

rersion 3.0 Page: 75 of 87

If newly started or dose modified or stopped during the first 12 weeks of study period	1633	Drugs for psychi atric disord ers	111	Antidepressants	112	Non-selective monoamine reuptake inhibitors	From 1st dose to 4 weeks after the last dose
If newly started or dose modified or stopped during the first 12 weeks of study period	1633	Drugs for psychi atric disord ers	111	Antidepressants	113	Selective serotonin reuptake inhibitors (SSRI)	From 1st dose to 4 weeks after the last dose
	45	Drugs interac ting with CYP3 A	240	CYP3A inducers	225	Moderate CYP3A inducers	From 1st dose to 4 weeks after the last dose Considered not to have an influence on efficacy, if route is auricular(otic), ophthalmic or conjunctival.
	45	Drugs interac ting with CYP3	240	CYP3A inducers	265	Strong CYP3A inducers	From 1st dose to 4 weeks after the last dose

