If newly started or dose modified or stopped during the first 12 weeks of	1633	Drugs for psychi atric disord ers	111	Antidepressants	1830	Antidepressant Serotonin Norepinephrine Reuptake Inhibitors (SNRI)	From 1st dose to 4 weeks after the last dose

version 3.0 Page: 76 of 87

study				
period				

^aIn this column, the terms "1st dose" and "last dose" both refer to the start date and stop date of certain doses of concomitant medication. If the dose was changed, a new start date and/or stop date were reported.

In addition, the following concomitant medications are considered prohibited:

Table 6–6: Preliminary list of prohibited concomitant medication by drug names (can be updated during the blind review meeting)

Any additional condition, so that considered as prohibited and considered as intercurrent event	WHO Drug Name	WHO Drug Record Number	WHO Drug Sequence Number 1	WHO Drug Sequence Number 2	Duration of impact with respect to efficacy ^a (considered up to 12 weeks ^b)
If newly started or dose modified or stopped during the first 12 weeks of study period	ARMOUR THYROID	000537	01	011	From 1st dose to 12 weeks after the last dose
If newly started or dose modified or stopped during the first 12 weeks of study period	NATURE THROID	000537	01	027	From 1st dose to 12 weeks after the last dose
If newly started or dose modified or stopped during the first 12 weeks of study period	LEVOTHYROXINE	000680	01	001	From 1st dose to 12 weeks after the last dose
If newly started or dose modified or stopped during the first 12 weeks of study period	L-THYROXINE	000680	01	006	From 1st dose to 12 weeks after the last dose
If newly started or dose modified or stopped during the first 12 weeks of study period	L-THYROXIN	000680	01	014	From 1st dose to 12 weeks after the last dose
If newly started or dose modified or stopped	LEVAXIN	000680	02	002	From 1st dose to 12 weeks after the last dose

^b No further differentiation if duration of impact is longer than 12 weeks since ICEs are considered in the analysis only for the first 12 weeks of the study.

^c Tamoxifen (ATC =L02BA), aromatase inhibitors (ATC = L02BG), GnRH agonists (DGCODEL1 = 108, DGCODEL2 = 109) GnRH antagonists (DGCODEL1 = 108, DGCODEL2 = 110)

Page: 77 of 87

	T	T	ı	ı	
during the first 12 weeks of study period					
If newly started or dose modified or stopped during the first 12 weeks of study period	SYNTHROID	000680	02	005	From 1st dose to 12 weeks after the last dose

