If newly started or dose modified or stopped during the first 12 weeks of study period	EUTHYROX	000680	02	007	From 1st dose to 12 weeks after the last dose
If newly started or dose modified or stopped during the first 12 weeks of study period	THYROXIN	000680	02	014	From 1st dose to 12 weeks after the last dose
If newly started or dose modified or stopped during the first 12 weeks of study period	LEVOTHYROXINE [LEVOTHYROXINE SODIUM]	000680	02	020	From 1st dose to 12 weeks after the last dose
If newly started or dose modified or stopped during the first 12 weeks of study period	THYREX	000680	02	028	From 1st dose to 12 weeks after the last dose
If newly started or dose modified or stopped during the first 12 weeks of study period	THYROHORMONE	000680	02	029	From 1st dose to 12 weeks after the last dose
If newly started or dose modified or stopped during the first 12 weeks of study period	Т4	000680	02	031	From 1st dose to 12 weeks after the last dose
If newly started or dose modified or stopped during the first 12 weeks of study period	LETROX	000680	02	046	From 1st dose to 12 weeks after the last dose
If newly started or dose modified or stopped during the first 12 weeks of study period	UNITHROID	000680	02	052	From 1st dose to 12 weeks after the last dose

ersion 3.0 Page: 78 of 87

	T		,		
If newly started or dose modified or stopped during the first 12 weeks of study period	LEVOTIROXINA [LEVOTHYROXINE SODIUM]	000680	02	054	From 1st dose to 12 weeks after the last dose
If newly started or dose modified or stopped during the first 12 weeks of study period	L-THYROXIN HENNING	000680	02	058	From 1st dose to 12 weeks after the last dose
If newly started or dose modified or stopped during the first 12 weeks of study period	TIROXIN [LEVOTHYROXINE SODIUM]	000680	02	062	From 1st dose to 12 weeks after the last dose
If newly started or dose modified or stopped during the first 12 weeks of study period	L THYROXIN	000680	02	070	From 1st dose to 12 weeks after the last dose
If newly started or dose modified or stopped during the first 12 weeks of study period	EUTIROX	000680	02	074	From 1st dose to 12 weeks after the last dose
If newly started or dose modified or stopped during the first 12 weeks of study period	LEVOTHYROXIN	000680	02	081	From 1st dose to 12 weeks after the last dose
If newly started or dose modified or stopped during the first 12 weeks of study period	TIROSINT	000680	02	087	From 1st dose to 12 weeks after the last dose

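### Read literally, stopping a stable, permitted antidepressant or thyroid drug during the first 12 weeks flags weeks completed before the stop as intercurrent events in the supplementary estimands

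*SAP*

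**What the plan says.** Protocol Table 10-4 (Section 10.6) lets a participant stay on an antidepressant that has been stable for at least 4 weeks and is prescribed for another disorder. Exclusion criterion 12 (Section 5.2) accepts treated hypothyroidism on a stable replacement dose. Both drug classes can therefore legitimately be in use at baseline.

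SAP 6.4.3 lists them in Tables 6-5 and 6-6 and counts them as an intercurrent event "If newly started or dose modified or stopped during the first 12 weeks of study period". Four combination thyroid entries at the end of Table 6-6 omit the stopping condition.

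The impact window for antidepressants is "From 1st dose to 4 weeks after the last dose". For thyroid products it is "From 1st dose to 12 weeks after the last dose". Footnote a says that first and last dose "both refer to the start date and stop date of certain doses of concomitant medication", and adds that a dose change leads to a new start and/or stop date being reported.

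Rule 1 of the same section states that "any intake of prohibited medication during Week 1 that has an effect on HF will be considered an intercurrent event". Rule 2 counts intake in Weeks 4, 8 and 12, and earlier intake still within washout.

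SAP 4.1.2 flags events occurring from start of treatment to Day 84. A week is flagged if the event occurs by its fifth day, and the flag persists if the impact ends on the third day of a week or later.

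**The concern.** For a stable drug that is later stopped, the triggering fact is the stop, but the window is anchored at first intake. Week 4 status then depends on something that happens after Week 4.

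The first supplementary estimand (SAP 4.2.3.1) discards the flagged data and imputes them. The second (SAP 4.2.3.2) replaces them with zero change from baseline. SAP 4.3.1.4 carries both to the key secondary endpoints. A wrongly flagged woman can also lose her place among the compliant participants who form the Pattern 1 reference group. The by-week event counts in SAP 4.1.3 inherit the flags, and the Kaplan-Meier plot of first prohibited medication may do so too.

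If stopping such a drug is related to treatment, for example because symptoms improve, the misclassification would differ by arm.

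**Working it through.** **The plan's own figure first.** The SAP gives no rate for this event. Its only relevant scale is Table 5-1: SD 3.632, N = 243 and 122, difference -1.50, one-sided alpha 0.025.

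- SE = 3.632 × √(1/243 + 1/122) = 0.403.
- Noncentrality = 1.50/0.403 = 3.72 on 363 degrees of freedom.
- Power from the noncentral t = 96.01%, as stated.

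**Date rule.** The analysed weeks are Week 1 (Days 2-8), Week 4 (22-28), Week 8 (50-56) and Week 12 (78-84). Under SAP 4.1.2, a week is flagged if the impact starts by its fifth day and ends on its third day or later. The impact ends at stop + 28 days (antidepressant) or stop + 84 days (thyroid). The start is either the record start (before Day 1) or the stop date.

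| Stop day | Drug | Flagged, record start | Flagged, stop date |
|---|---|---|---|
| 10 | antidepressant | 1, 4 | 4 |
| 40 | antidepressant | 1, 4, 8 | 8 |
| 40 | thyroid | 1, 4, 8, 12 | 8, 12 |
| 66 | either | 1, 4, 8, 12 | 12 |
| 70 | antidepressant | 1, 4, 8, 12 | 12 |

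In the Day 70 case the window ends on Day 70 + 28 = Day 98. Three of the four flagged weeks precede the stop. In the first supplementary analysis, this leaves only baseline, arm and stratum as the woman's own information for imputation.

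The fifth day of Week 4 is Day 26. A window starting on Day 27 or later therefore never flags Week 4, but the record-start window always does. That covers 84 - 27 + 1 = 58 of the 84 possible stop days.

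**Dose change on Day 66.** Using only the new-dose record flags Week 12. Weeks 1, 4 and 8 are added only if the closed old-dose record is also treated as a stop.

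**Size in the second supplementary analysis.** All rates and mean changes here are assumptions.

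- With a fraction *f* wrongly set to zero, an arm mean moves by *f* × mean change. Take *f* = 0.25-3% and mean changes of -6 (elinzanetant) and -4 (placebo). The arm means move by 0.015-0.18 and 0.01-0.12.
- At equal rates the difference moves by 0.005-0.06 towards zero. The upper end is 0.06/0.403 = 0.15 SE.
- If 3% of the elinzanetant arm and none of the placebo arm were affected, the shift would be 0.18, or 0.45 SE.
- More broadly, with 1-10% of both arms set to zero, a true -1.50 becomes -1.485 to -1.35. Power falls from 96.0% to 95.7-91.6%, with the SD held fixed.

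**The case against.** The best defence is SAP 4.1.2. It governs this event by name, considers events from start of treatment onward, and flags forward from the week of occurrence. A stop on Day 70 first satisfies the table's condition on Day 70, so forward flagging is a fair reading. Dating the event at a pre-baseline first intake would put it outside the flagging period and give zero or negative time in the time-to-event formula. This shows that the text can be read sensibly, and it is why the Kaplan-Meier effect is only possible. It does not settle the matter: 4.1.2 never says that the event date is the stop date, while the specific tables, footnote a and rule 1 are all keyed to intake.

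The tables are also labelled preliminary, and 6.4.3 provides for manual review and blinded finalisation of the time periods. That offers a route for the correction but does not supply the rule. The two later SAP supplements do not touch 6.4.3.

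A reader might go further than the documents allow in three ways.

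- **Dose changes.** It is tempting to say that they back-flag in the same way. Footnote a provides for a new start and/or stop date, so this depends on how the old record is treated. The text is ambiguous.
- **Hormones.** They are not a permitted stable drug. Protocol Table 10-4 prohibits oestrogen and progestin products from before baseline and allows no stable use.
- **Vaginal hormones.** The SAP's "From 1st dose to 4 weeks after the last dose if the route is vaginal, intravaginal, cutaneous, nasal or transdermal" might seem to contradict the protocol's "From 1 week prior to Baseline Visit". The first is an assumed on-study impact duration and the second a pre-baseline prohibition period, so the difference alone is not a contradiction.

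**Conclusion.** The point holds for an antidepressant, or a thyroid product whose entry includes stopping, that is permitted, stable since before baseline and stopped in the first 12 weeks. The literal rule flags weeks completed before anything changed, and the general rule does not clearly override it. Two programmers could follow the SAP and derive different Week 4 data sets.

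A reader might infer that the primary result is at risk. It is not: the main estimand uses treatment policy for every intercurrent event, and the main analysis of the key secondary endpoints follows it. The damage is limited to the supplementary estimands for those endpoints, the Pattern 1 reference group, the by-week event counts and possibly the Kaplan-Meier plot.

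The numerical effect is likely small, at most 0.06 hot flashes per day under the equal-rate assumptions above. It could be larger if stopping differs by arm, but nothing in the documents shows that it does. The change is still worth making, because the rule as written discards or zero-scores valid data.

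**What to change.** In SAP 6.4.3, keep the first-dose start for newly started drugs. For a drug stable since before baseline, state that the impact window starts on the date of the dose change or stop, and that weeks completed before that date are not flagged. Say explicitly that a closed old-dose record does not reopen earlier weeks. Align SAP 4.1.2, footnote a and Tables 6-5 and 6-6 with this, and settle it at blind review before unblinding.

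Separately, SAP Table 6-5 counts oestrogens and progestogens only when started, changed or stopped, while protocol Table 10-4 prohibits them outright. These passages must be reconciled.

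The cost is one sentence and one derivation rule for the window, plus the hormone reconciliation. No new data are needed.

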6.4.4. Interruption or discontinuation in intake of adjuvant endocrine therapy

Interruption or discontinuation in intake of adjuvant endocrine therapy will be defined by comparing tablets taken during baseline for two weeks and at selected weeks as follows:

For participants using tamoxifen: reduction of at least 50% of planned daily dosage (tablets taken during the 14 days prior start of treatment, i.e. during baseline) taken during week1, weeks 3 and 4, weeks 7 and 8 or weeks 11 and 12 compared to baseline.

For participants using aromatase inhibitor: reduction of at least 30% of planned daily dosage (tablets taken during the 14 days prior start of treatment, i.e. during baseline) taken during week1, weeks 3 and 4, weeks 7 and 8 or weeks 11 and 12 compared to baseline.

6.5. Appendix 5: Population characteristics

In general, descriptive statistics by treatment group and overall will be presented for variables defined in this section. For continuous variables, number of observations, mean, standard deviation, minimum, median, and maximum will be presented. For categorical variables, number and percentage of participants will be presented. Listings will be provided as appropriate.

6.5.1. Demographics and baseline characteristics

All demographic and baseline characteristics will be summarized by treatment group and overall. The descriptive statistics will be presented for the SAF and FAS.

Demographic and baseline assessments to be summarized will include:

- Population type (breast cancer, high-risk for developing breast cancer)
- Type of treatment for the pre-existing condition at baseline (tamoxifen, aromatase inhibitors)
- Duration of adjuvant endocrine therapy (from initiation of the therapy until baseline visit)
- Age (at inclusion), region/country, race, ethnicity
- Categorized age
 - o <40 years, 40-49 years , 50-59 years, 60-65 years, >65 years

^b No further differentiation if duration of impact is longer than 12 weeks since ICEs are considered in the analysis only for the first 12 weeks of the study.

version 3.0 Page: 82 of 87

- Weight (kg), height (cm), body mass index (BMI; kg/m²)
- Categorized BMI ($< 18.5, 18.5 \text{ to } < 25, 25 \text{ to } < 30, \ge 30 \text{ kg/m}^2$)
- Smoking history (Never, Former, Current)
- Level of educational

Demographic and baseline characteristics will be summarized also for the following subgroups:

- Type of treatment for the pre-existing condition at baseline (tamoxifen, aromatase inhibitors)
- Race
- Ethnicity
- Smoking history (Never, Former, Current)
- BMI ($< 18.5, 18.5 \text{ to } < 25, 25 \text{ to } < 30, \ge 30 \text{ kg/m}^2$)

6.5.2. Reproductive and Menstrual History and Breast cancer classification at baseline

Reproductive and menstrual history will include information on number of pregnancies, number of births and years being amenorrheic and number of participants with hysterectomy or oophorectomy. Hysterectomy or oophorectomy are based on Prior and concomitant procedures -CRF. (For hysterectomy the PTs Hysterectomy, Hysterosalpingectomy, Hysterosalpingo-oophorectomy and Radical hysterectomy are considered. For oophorectomy the PTs Hysterosalpingo-oophorectomy, Oophorectomy, Oophorectomy bilateral, Salpingo-oophorectomy, Salpingo-oophorectomy bilateral, Salpingo-oophorectomy unilateral are considered.)

Breast cancer classification will include information on time from initial diagnosis, histology, laterality, stage and grading of the disease.

These variables will be analyzed descriptively, separately for each treatment group and overall based on the SAF and FAS.

